Phase 1: Pre-Implementation (Months 0-8). The PHQ-9 and fidelity measures will be embedded in the EHR and the PHQ-9 linked to tablet computers for client completion to promote feasibility. Phase 2: Randomized Implementation Trial: Dynamic Waitlist Control (Months 8-38; Sites:  $N=12$ ; Clinicians:  $N=150$ ; Clients:  $N=500$ ; mixed within- & between-subjects design). MBC implementation will occur across 4 cohorts (2-4 sites) at early and later stages (each with 5-months active implementation, 10-months sustainment) to reduce confounds (timing) and increase feasibility (phased training). Both conditions will enact the 5 strategies within the active implementation period. We will use rapid ethnography (month 1) to synthesize the needs assessment data and develop the tailored content. Phase 3: Characterization of MBC Fidelity (Months 38-48). MBC fidelity will be coded, clinician and client fidelity reports will be triangulated, and sustainment will be evaluated.

**Specific Aims.** The hybrid design yields one co-primary aim (outcomes at the clinician- and client-levels) and two secondary exploratory aims in the context of a pragmatic trial (Thorpe et al., 2009).

**Aim 1:** To compare the effect of standardized versus tailored MBC implementation on clinician-level (**1a**) and client-level (**1b**) outcomes. We hypothesize that tailored implementation will outperform standardized in terms of (**H1a**) MBC fidelity, and (**H1b**) reducing client depression severity.

**Aim 2:** To identify contextual mediators of MBC fidelity. We hypothesize (**H2**) that contextual mediators (structure, norms, etc.) will be leveraged in the tailored condition, but serve as barriers in the standardized condition.

**Aim 3:** To explore the impact of MBC fidelity on client outcomes (Chambers et al. 2013). We hypothesize (**H3**) that adapted MBC protocols (tailored condition) will outperform weekly administration of PHQ-9s (standardized condition) with respect to clinically significant change in depression severity from intake to week 12.

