**Implementation.** We then piloted a standardized implementation protocol consisting of (a) embedding the PHQ-9 into the electronic health record (requiring the clinician to verbally assess clients as tablets were not available), (b) a site-specific guideline for PHQ-9 use, and (c) a brief training. The 4-hour training content was based on the work of Persons, Hong, and Koerner (2012); topics included: MBC as a foundational framework; MBC clinical utility; the research evidence for MBC and the PHQ-9; the MBC protocol; research and IT supports to enact the protocol; introduction to the electronic health record interface; and steps for working with lack of progress. These strategies reflect a minimum set of discrete evidence-based implementation strategies that could be blended to facilitate implementation. Pre-training Intention to Use MBC scores were highly correlated with the frequency of subsequent PHQ-9 administration ( $r=.67$ ,  $p=.036$ ). Across sites, 67% MBC penetration was achieved (number of clinicians implementing MBC/number of participating clinicians). Site A achieved 44% penetration while Site B achieved 80% penetration. One limiting factor at Site A was technology problems as the new electronic health record had not yet been introduced and the PHQ-9 did not consistently show up for clinicians. Despite these relatively high penetration scores at the clinician level, this minimal standardized implementation protocol and site-specified MBC guideline resulted in 13.4% (Site A) and 38.6% (Site B) use of the PHQ-9 (by dividing number of administrations by total possible number of administrations) over the course of one year follow up. Unfortunately, we were unable to assess the differential effect of MBC implementation on client outcomes to determine whether adapted guidelines limited MBC's utility. These findings support the proposal in three ways: (a) they emphasize the utility of a

mixed methods needs assessment in identifying site differences in barriers, (b) they highlight the importance of tailoring strategies to barriers as this minimal standardized protocol led to superior outcomes in Site B where fewer barriers were present, and, (c) they underscore the potential importance of incorporating technologically advanced solutions for client PHQ-9 completion.

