**Phase 2: Randomized Trial: Implementation & Sustainment.** Implementation will take place across 12 sites in months 8-38 using the dynamic waitlist control design (Brown et al., 2006; C15. Justification and Feasibility). Specifically, matched sites (based on size and urban/rural status) will be randomized to either early or later stage implementation in 4 cohorts (2-4 sites per cohort spaced 5 months apart), with half the sites randomized to the standardized and half to the tailored condition; see Figure 2 for a concise depiction of the implementation timing. The timing of this protocol is based on the published work of Miller et al. (2012) as well as the successful naturalistic MBC implementation at Group Health (personal communication, [name], February 11, 2014). Beginning at month 8, the earliest cohort (2 sites) will engage in the baseline mixed methods needs assessment (Assessment Time 1; AT1). Using purposeful sampling (Palinkas et al., 2013), a subset of clinicians (N=5-8 at each site) representing extreme variation (nominated by clinic directors based on their support for or against MBC implementation) will participate in a 1.5-hour focus group. This sampling approach is critical to gain a wide range of clinician views. Rapid ethnography will then be used to uncover site-specific insights that will guide the content of training and consultation in the tailored condition only (with the aid of mixed method expert [name]; C13b. Data Analysis Plan). During the needs assessment, all enrolled clinicians will complete the battery of baseline measures (see Table 5, Section II), from which the opinion leader (Childers, 1998) and self-nominated MBC champion will be identified and invited to join the implementation team. Across conditions, this team will convene triweekly during the 5-month active implementation period to ensure implementation strategy fidelity (Proctor et al., 2013) and review MBC fidelity. Following the needs assessment, clinicians will participate in a 4-hour MBC training workshop (see C9. Pilot Studies for content) and will begin triweekly consultation. To characterize the differences in implementation team meetings and consultation between conditions, sessions will be audiorecorded and contextual factors logged by graduate research specialist on the MBC Barriers Log (informed by the Framework for Dissemination; [name] et al., 2008; see Appendix for form template). Simultaneously a site team member will log meetings (using the same form) and data triangulated to calibrate site team members and prep for the exit of research personnel. Implementation/Process Evaluations ([name] et al., 2008; AT2) at the clinician level will occur 5 months after the needs assessment at which point the research personnel will be removed. The site implementation teams will be encouraged to continue meeting to promote MBC sustainment and the responsibility to log and address MBC barriers will transfer completely to the site team members. Outcome/Impact Evaluation ([name] et al., 2008; AT3) at the clinician and client level will occur 10 months after the Implementation/Process Evaluation. Focus groups will be held with the implementation team at AT3 to review their experience and the site's progress since the research personnel exited the team. All aforementioned steps will be repeated across the remaining three cohorts.

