**Aim 1: Hypotheses:** Tailored implementation will outperform standardized in terms of (H1a) fidelity. MBC clinician fidelity was evaluated with two variables: (1) whether the PHQ-9 was recorded in the EHR, and (2) among encounters for which the PHQ-9 was recorded, whether it was discussed. Both outcomes were modeled using generalized linear mixed models with a logit link function for a binary distribution using the lme4 package. All models included random intercepts for clinicians and patients. Models for both outcomes were constructed in an identical sequence. Models comparisons in the model-building sequence described below were evaluated using the Bayesian Information Criterion (BIC); the model with the better BIC was selected for presentation. Several unconditional growth models (i.e., models with only parameters for time) were fit (i.e., linear, quadratic, log-transformed number of months). After establishing the unconditional growth model, additional fixed effects were added in the following sequence: (1) group main effect and (2) group x time interaction. Finally, new versus existing patient status was investigated as a main effect using a dummy variable for new patient status and as a patient status x group interaction.

**Aim 2: Hypotheses:** Contextual mediators will be leveraged in the tailored condition, but serve as barriers in the standardized condition. Mediation models were fit to evaluate which contextual factors (based on clinician-completed surveys, Table 5; and, clinician selection of drop-down menu reasons for MBC deviations captured in the electronic health record) mediate the impact of the implementation condition on both clinician- and client-level outcomes. The two critical effects underlying mediation were evaluated in separate models: treatment condition predicts the mediator (path *a*) and the mediator predicts the outcome (path *b*). Specifically, mediators were assessed at the conclusion of the implementation window and the mediators were used to predict PHQ9 completion in the sustainment window. The *a* path was assessed using linear mixed models with Satterthwaite degrees of freedom

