#### **C14. Potential Problems & Alternative Strategies.**

Our hypothesis is that tailored implementation will outperform the standardized approach. However, it is possible that this hypothesis will not be supported. Findings of this nature would not be undesirable, but rather would illustrate that while emerging research suggests the need to contextualize implementation interventions (Fixsen, 2005; Wallerstein & Duran, 2010), this customization compromises ultimate outcomes—a critical realization for the field of implementation science. Furthermore, if we are unable to detect mediators of implementation and effectiveness outcomes included in this proposal, it may suggest the need to re-evaluate the *Framework of Dissemination*. Specifically, putative mediators of the dissemination and implementation process not included in this model might require empirical investigation. Our qualitative analyses will allow for careful examination of unanticipated mediators. At the level of the clinician, we anticipate substantial variability in competency and general approach to psychotherapy. However, we are not concerned about the effects of this variability on study outcomes because (1) randomization should result in equivalent variability across conditions and (2) MBC is conceptualized as transtheoretically relevant, regardless of the therapist’s orientation or training.

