#### **Phase 2 (Months 8 – 38)**

*5-Month Active Implementation.* Beginning at month eight, clinicians who provide individual psychotherapy to adults with depression (based on their self-reported typical and current caseload (i.e., clinicians will learn in the eligibility discussion that if they consent to participate in the study then they must have eligible clients to potentially enroll as well) and who conduct psychotherapy sessions in English will engage in the baseline mixed methods needs assessment. This assessment will consist of a battery of surveys and then, following the completion of these surveys a focus group will take place. Clinicians will be asked to complete the following baseline battery of self-reports (Appendix A): Demographic Questionnaire ([name] & Simons, 2011; Appendix A.1); Progress Monitoring Theory of Planned Behavior (Francis et al., 2004; Appendix A.2); Attitudes toward Standardized Assessment-Monitoring and Feedback (Jensen-Doss et al., *in press*; Appendix A.3); Monitoring and Feedback Attitudes Scale (Jensen-Doss et al., *in press*; Appendix A.4); Monitoring As Usual Measure (Lyon et al., 2015; A.5); Evidenced-Based Practices Attitudes Scale (Aarons, 2004; A.6); Survey of Organizational Functioning (Broome et al., 2007; A.7), Implementation Climate (Jacobs et al., 2014; A.8); Implementation Climate Scale (Earhart et al., 2014; A.9); Barriers and Facilitators to Implementing Survey (Salyers, Rollins, McGuire, & Gearhart, 2008; A.10); Sociometric Questionnaire (Valente et al., 2007; A.11); Opinion Leadership Scale (Childers, 1986) and self-nomination question (A.12); Implementation Leadership Scale (Aarons et al., 2014; A.13); and Perceptions of Adopting Measurement-Based Care (Moore & Benbasat, 1991; A.14). All questionnaires will be completed online using assessment software by emailing them a link or via hard copy (in-person). These questionnaires will take about 60 minutes to complete and clinicians who complete the baseline assessment will receive \$50 compensation. Using the data from these surveys, a subsample of clinicians at each site, selected using purposeful sampling for extreme variation (Palinkas et al., 2013), will be asked to participate in a 1.5 hour focus group (Appendix E.1). Clinicians who participate in the focus group(s) will receive \$25 compensation. Focus groups will be recorded and transcribed with data de-identified for the purposes of qualitative coding. Staff who do not provide individual psychotherapy to adults with depression in English (for example, this could be clinicians who primarily provide therapy to children, groups, diagnoses other than depression and/or conduct therapy in another language; or psychiatrists, nurses, nurse practitioners, case managers, other non-clinical staff) will engage in an abbreviated version of the battery of self-report measures which will include: (Appendix A): Demographic Questionnaire ([name] & Simons, 2011; Appendix A.1); Progress Monitoring Theory of Planned Behavior (Francis et al., 2004; Appendix A.2); Attitudes toward Standardized Assessment-Monitoring and Feedback (Jensen-Doss et al., *in press*; Appendix A.3); Monitoring and Feedback Attitudes Scale (Jensen-Doss et al., *in press*; Appendix A.4); Evidenced-Based Practices Attitudes Scale (Aarons, 2004; A.6); Sociometric Questionnaire (Valente et al., 2007; A.11); Opinion Leadership Scale (Childers, 1986). All questionnaires will be completed online using assessment software by emailing them a link or via hard copy (in-person). The questionnaires will take less than 30 minutes to complete and staff who complete the abbreviated baseline assessment will receive \$20 in compensation per assessment point. Note, from this point forward we will refer to this group of staff as the “general staff” to differentiate them from those completing the full baseline battery which we will refer to as simply “clinicians.”

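### The co-primary fidelity models (H1a) adjust for no pre-implementation clinician measure, although the trial plans to collect suitable ones; adjusting would cost little and could add modest precision

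*Combined protocol and SAP*

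**What the plan says.** Section A makes fidelity one half of the main aim: "The hybrid design yields one co-primary aim (outcomes at the clinician- and client-levels". For H1a, Section C13a (Aim 1) describes two logit mixed models, one for whether the PHQ-9 was recorded and one for whether a recorded score was discussed. "All models included random intercepts for clinicians and patients". Time terms are chosen first, then "additional fixed effects were added in the following sequence: (1) group main effect and (2) group x time interaction". Last, "new versus existing patient status was investigated as a main effect using a dummy variable for new patient status", together with its interaction with group. BIC decides which model is presented.

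Section C11 (Phase 2) plans that "all enrolled clinicians will complete the battery of baseline measures (see Table 5, Section II". Section C12a places this assessment, AT1, before implementation. The clinician battery in Section VII includes a theory-of-planned-behavior measure (Appendix A.2) and the "Monitoring As Usual Measure" (Appendix A.5). In Section C13a the clinician surveys appear only as Aim 2 mediators, assessed when the implementation window closes.

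Section C9 reports from the pilot: "Pre-training Intention to Use MBC scores were highly correlated with the frequency of subsequent PHQ-9 administration" (r = .67, p = .036). On differences between clinicians in competency and approach, Section C14 says that "randomization should result in equivalent variability across conditions".

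**The concern.** Twelve sites are randomised, six per arm. With so few units, the arms can differ by chance in how ready their clinicians are to use the PHQ-9. A model without a readiness measure leaves that difference in the fidelity contrast and leaves explainable clinician variance in the error.

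The plan's own pilot suggests that readiness may matter. Its two sites differed on social influence (p = .042) and self-efficacy (p = .010), and later on PHQ-9 use (13.4% versus 38.6%). A measure of the same kind is planned for every enrolled clinician, so the information would go unused in the analysis where it could help most. At stake is the precision of one co-primary contrast.

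**Working it through.** **Inputs.** Section C13a (Power calculations): N = 150 clinicians, two-sided .05, power above 80%, ICC .50 within participant and .05 within site, 5% more missing per wave, detectable d = .46. Section C11: 12 sites, half per arm. Section C9: r = .67, p = .036.

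**1. The plan's figure.** A plain two-sample comparison needs 2 x (1.960 + 0.842)^2 / .46^2 = 74.2, so 75 per arm; power is 80.4%. The group x time contrast with three waves at 0, .5 and 1 and residual variance .50 gives the same size. The slope variance per clinician is .50/.50 = 1, so the detectable difference is 2.802 x sqrt(2 x 1/75) = .457, or .46 to .48 with the stated dropout. The site intercept cancels from this contrast. So .46 reproduces, but not as an average-level group contrast carrying the site ICC (step 3).

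**2. The pilot correlation.** Its n is not given. With t = r x sqrt((n-2)/(1-r^2)), r = .67 gives p = .048 at n = 9, .034 at n = 10, .024 at n = 11 and .0003 at n = 24. The reported .036 therefore implies n of about 10. The Fisher interval at n = 10 is tanh(.811 ± 1.96/sqrt(7)), which is .07 to .91.

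**3. Average-level contrast.** Assumed shares: site s = .05, clinician c = .45, residual e = .50. There are 12.5 clinicians per site (150/12), 75 per arm, and three waves (225 observations per arm).

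Detectable d = 2.802 x sqrt(2 x [s/6 + c/75 + e/225])

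Unadjusted: 2.802 x sqrt(2 x [.00833 + .00600 + .00222]) = .51. With t on 10 df the multiplier is 2.228 + 0.879 = 3.107, giving .57.

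A covariate with correlation r multiplies c, or c and s, by 1 - r^2. At r = .67, 1 - .449 = .551. Normal results, with 10 df in brackets:

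| r | clinician variance only | clinician and site |
|---|---|---|
| 0 | .510 (.565) | .510 (.565) |
| .07 | .509 (.565) | .509 (.564) |
| .30 | .501 (.556) | .490 (.543) |
| .67 | .466 (.517) | .399 (.442) |

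Power at d = .46 goes from 71% (63%) unadjusted to 79% (70%) or 90% (83%) at r = .67.

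**4. Group x time.** In step 1 its variance depends only on the residual within clinicians. The main effect of a score fixed over time does not reduce that, so this term gains nothing.

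**5. Chance imbalance.** The SE of the arm difference in a baseline score is sqrt(4 x [1 + 11.5 x ICC]/150), ignoring matching. For an assumed covariate ICC of 0, .05 and .20 this is .16, .20 and .30 SD. The chance of an imbalance above .2 SD is 22%, 33% and 50%.

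All of this is a linear, three-wave guide to logit models fitted to encounters.

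**The case against.** The strongest reply is that a randomised contrast needs no adjustment. Chance imbalance is sampling error, and a correctly clustered standard error already allows for it. That stands, and it limits the point to precision. Matching on size and urban/rural status, and the randomisation checks under Data screening, help a little. Neither uses a readiness measure, and no action is attached to a failed check.

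The evidence for the covariates is also thin. The .67 rests on about ten clinicians at two sites, one of which had technology failures, so it may partly reflect site. That the trial's theory-of-planned-behavior measure contains an intention scale is inferred from its name; Table 5 describes a measure from the same manual only as three norms items, and does not list the Monitoring As Usual Measure. No document links the latter to later fidelity. The pilot used a standardised protocol, while H2 expects contextual factors to act differently in the two arms, so a common slope may recover less. All this stands against promising a gain, though not against naming the covariates in advance.

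Timing is a fair challenge. Section V puts site randomisation just before Phase 2, Section VII starts the battery at month eight, and later cohorts follow at five-month intervals. AT1 may therefore come after allocation. It still precedes training.

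Completion is not assured either. In Section XII, returning the paper battery is the act of consent, but on the web route consent comes before the questions.

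Finally, Aims 1 to 3 are written in the past tense and Aim 3 reports 22.8% missing at week 12. Outcomes may already have been seen, which bears on how an adjusted result is labelled.

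**Conclusion.** The omission is real: neither H1a model contains a clinician measure taken before implementation. The loss is of efficiency. The detectable average-level contrast could fall from about .51 to between .47 and .40 at r = .67, to about .50 at r = .30, and not at all near r = .07. These figures rest on the assumed variance split and on a site term, which the H1a text does not list. The benefit is to the group main effect only.

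A reader might infer more in two ways, and the documents support neither.

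- Shrinking the stated effect directly, .46 x sqrt(1 - .67^2) = .34, treats all variance as explainable. The plan's own ICC of .50 leaves half within participants. The .46 also matches the group x time contrast, which a baseline main effect does not sharpen, and not an average-level contrast carrying the site ICC.
- Multiplying a typical imbalance of .20 SD by .67 gives .14 SD, about 30% of .46, which could be read as a bias. It is ordinary sampling error, and the .67 is itself very uncertain.

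The change is worth making because it is cheap and uses measures already planned; a large gain cannot be promised.

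**What to change.** In Section C13a, Aim 1:

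- Enter the AT1 theory-of-planned-behavior score (its intention scale, if the instrument has one) and the AT1 Monitoring As Usual score as fixed effects in both H1a models, before group. Keep them regardless of BIC.
- Impute missing scores under the Missing data paragraph.
- State that AT1 is measured before training, and whether clinicians then knew their site's condition.
- Report the unadjusted contrast alongside. Give both as marginal risk differences, because covariate adjustment in a logit model changes the conditional odds ratio as well as its precision.
- If outcome data have already been examined, label the adjusted result a sensitivity analysis.

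The cost is a few sentences and two clinician-level parameters among about 150 clinicians; no new data are needed. The downside is a covariate that may be recorded after site allocation, which the unadjusted result lets the reader judge.

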## C6. MBC Fidelity

In this proposal, fidelity to MBC is a three-level categorical variable defined by (a) client completion of the PHQ-9 (No=0, Yes=1), (b) clinician review of scores in the electronic health record (No=0, Yes=1), and (c) discussion of scores in session (No=0, Yes=1). The former two (PHQ-9 completion and clinician review of scores) will be automatically captured through the electronic health record. Clinicians will also check a box in the electronic health record progress note to indicate if they discussed scores in session, as this practice optimizes the effectiveness of MBC (Eisen, Dickey, & Sederer, 2000). Given the known limitations to clinician self-report, this latter fidelity criterion will also be assessed with client self-report via an automated telephone survey immediately after their session. In their first month of implementation, all clinicians (regardless of condition) will be asked to indicate factors they perceived to have limited MBC use. Through a drop-down menu embedded in the electronic health record progress note, clinicians will select contextual factors based on the literature (Dowrick et al., 2009; Garland, Kruse, & Aarons, 2003; Valenstein et al., 2009) and clinician-identified factors (from our pilot data); See Appendix for complete list of options (e.g. lack of time, client refused, clinician forgot).

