implemented using the R lmerTest package with a random intercept for clinic. The b path was assessed using generalized linear mixed models with a logit link function for a binary distribution using the lme4 package. **Aim 3 Hypotheses:** Adapted MBC protocols (i.e., tailored condition) will outperform routine weekly administration of PHQ-9s (i.e., standardized condition) with respect to clinically significant change in depression severity from intake to week 12. Depression severity was analyzed using linear mixed models with Satterthwaite degrees of freedom implemented using the R lmerTest package. Multiple imputation was used to estimate missing values across 20 datasets in which 22.8% of patients did not complete the 12-week interview. We first assessed whether there was a change in PHQ-9 between intake and week 12 in a mixed model containing patient status as a covariate and random intercepts for patient and clinic. Next, implementation group was added to the model. In addition, number of sessions, number of sessions that the PHQ-9 was recorded, and number of sessions that the PHQ-9 was discussed were added to the model. We also examined the interactions between new patient status and the focal variables. **Power calculations.** A power analysis for the multilevel models for Aim 1 was assessed with Monte Carlo studies in which power is the proportion of significant effects (2-tailed  $\alpha$ ,  $p < .05$ ) for parameters of interest observed over repeated analyses of simulated data (Muthén & Muthén, 2002; Thoemmes, Reiser, & MacKinnon, 2010) using MPlus (version 7). For each model, 10,000 data sets were simulated and analyzed. Data in the Monte Carlo studies were simulated with the goal of identifying the smallest detectable effect size with power  $> 80$ . Dropout was simulated to reflect an increase of 5% missing data per wave. Repeated measurements were nested within participants (ICC = .50) and participants were nested in sites (ICC = .05). Average effect sizes for Aim 1 analyses were computed using an approximation of Cohen's  $d$  for growth models (Feingold, 2009). Using this metric, we are sufficiently powered to detect effect sizes as small as  $d = .46$  for the clinician models ( $N = 150$ ) and effect sizes as small as  $d = .30$  for the client models ( $N = 500$ ). For Aim 2, we conducted power analyses for the hypothesized mediation effects with the same assumptions described above but with the use of effective samples size estimates (an ICC corrected sample size) based on a design effect adjustment (Bickel, 2007) in order to use standard effect size metrics. The  $\kappa^2$  effect size for mediation (.01, .09, and .25 represent small, medium, and large  $\kappa^2$  respectively) was computed (Preacher & Kelly, 2011). We are sufficiently powered to detect effect sizes as small as  $\kappa^2 = .16$  for the clinician models and effect sizes as small as  $\kappa^2 = .10$  for the client models. For Aim 3 analyses, we are sufficiently powered to detect effect sizes as small as  $r = .27$  for clinicians and as small as  $r = .21$  for clients. The planned sample sizes are consistently sufficient for detecting medium effect sizes for clinician outcomes and small effect sizes for client outcomes, with the power to treat site as a random effect based 6 sites per condition (Atkins & Baldwin, 2013).

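### As described, path b of the Aim 2 mediation analysis gives one mediator slope pooled over arms; the arm-specific effect in H2 is not tested quantitatively, and b is not adjusted for condition.

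*Combined protocol and SAP*

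**What the plan says.** Section A (Aim 2) states H2 as: "contextual mediators (structure, norms, etc.) will be leveraged in the tailored condition, but serve as barriers in the standardized condition". Section C13a repeats it under Aim 2 and sets out to find which contextual factors "mediate the impact of the implementation condition on both clinician- and client-level outcomes".

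The method is short. "The two critical effects underlying mediation were evaluated in separate models". Path a regresses the mediator on condition in a linear mixed model with a clinic random intercept. Path b uses mediators measured at the end of the implementation window to predict PHQ-9 completion in the sustainment window: "The b path was assessed using generalized linear mixed models with a logit link function for a binary distribution". No covariates and no random effects are listed for path b. Under Aim 1 in the same section, the group x time and patient status x group interactions are named.

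The power text in C13a gives detectable mediation effects of kappa-squared .16 (clinician models) and .10 (client models), and says nothing about a moderated effect. Section C13b plans a qualitative comparison, between conditions, of the valence of contextual themes.

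**The concern.** H2, read at face value, is about moderation of the mediator-outcome relation: the same factor helps in one arm and hinders in the other. A single pooled slope cannot show that. It averages the two arm-specific slopes, and the average may be near zero, diluted, or dominated by one arm.

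There is a second problem that does not depend on that reading. In any mediation analysis of a randomized condition, the mediator slope has to be estimated with condition in the model. Otherwise a mediator that merely differs between arms picks up part of the direct effect of condition on the outcome.

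At stake is the interpretation of Aim 2: a factor that works in opposite directions could be reported as unimportant, and a factor that does nothing could be reported as a mediator.

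**Working it through.** **1. The plan's own figures.** The only Aim 2 figures are the detectable kappa-squared values. Mean cluster sizes are 150/12 = 12.5 clinicians and 500/12 = 41.7 clients per site. With the stated site ICC of .05, the design effects are 1 + 11.5 x .05 = 1.575 and 1 + 40.67 x .05 = 3.033. Effective sample sizes are 150/1.575 = 95.2 and 500/3.033 = 164.8. Assuming a = b, no direct effect and a joint-significance test, 80% power falls near kappa-squared .11 (clinicians) and .06 (clients), against the stated .16 and .10. The plan gives neither the split between a, b and the direct effect nor the test, so its values can be neither confirmed nor called wrong. They do not cover an interaction.

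**2. What a mediator-only path b estimates.** Suppose the arms are equal in size, the mediator has the same spread in each, and condition has no effect on mediator level or directly on outcome. On a linear scale the pooled slope is then (b_T + b_S)/2, where T is tailored and S is standardized. Large-sample logistic fits (400,000 rows) give nearly the same. Rejection rates are for 150 clinicians in 12 sites with 20 encounters each, mediator site ICC .05, clinician variance 1.0 and site variance 0.09 on the logit scale, analysed without a site term. Slopes, encounters and outcome variances are assumptions, as the documents give none.

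| b_T / b_S (log-odds per SD) | Simple average | Fitted pooled slope | Pooled slope significant | Condition x mediator significant |
|---|---|---|---|---|
| +0.5 / -0.5 | 0 | 0.00 | 7% | 99.9% |
| +0.3 / -0.3 | 0 | not run | 6.5% | 86% |
| +0.8 / -0.3 | 0.25 | 0.21 | 61% | 99.9% |
| +0.5 / 0 | 0.25 | 0.24 | 71% | 71% |
| +0.25 / +0.25 | 0.25 | 0.25 | 74% | 6% |

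Equal and opposite slopes cancel. Unequal ones do not: +0.8/-0.3 is reported as one positive slope for both arms, which hides the barrier. The last two rows show that the pooled model cannot separate an effect confined to one arm from a uniform effect. Adding condition only as a main effect leaves the +0.5/-0.5 slope at 0.00.

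**3. Bias from omitting condition.** With no mediator effect in either arm, a mediator shift a (in SD) and a direct effect c (log-odds), the linear approximation for the spurious slope is c x (a x .25)/(1 + a² x .25).

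- a = .46, c = .5: .5 x .115/1.0529 = .055; logistic fit .05.
- a = .5, c = .5: .5 x .125/1.0625 = .059.
- a = .8, c = 1.0: .20/1.16 = .172; logistic fit .17.

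With condition in the model, the fitted slopes return to about 0.

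**4. Power of the added interaction.** This depends heavily on clinician variance. With 10 encounters per clinician, no site clustering and opposite slopes of .2, .3 and .4, a clinician variance of 0.5 (latent ICC .5/(.5 + 3.29) = .13) gives about 68%, 95% and over 99%. Carrying the plan's repeated-measures ICC of .50 to the logit scale (variance 3.29, an assumed translation) gives about 21%, 41% and 67%.

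**5. Related passages set side by side.**

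- Client level: C13a promises and powers client-level mediation, but PHQ-9 completion is the only path-b outcome named. The Aim 3 model adds session counts and no contextual mediators.
- Deviation reasons: C13a lists them as mediators. Section C6 ties them to the start ("In their first month of implementation, all clinicians (regardless of condition) will be asked to indicate factors"), and C12a also says the first month. The fidelity row of Table 5, which includes these reasons, gives baseline, AT2 and AT3, and Section VII has clinicians at affected sites recording on paper weekly.
- Instruments: Table 5 names the Organizational Culture Scale, the Infrastructure Survey and the Organizational Resources Scale. None is in the battery that Section VII lists for clinicians. C13a still points to Table 5.

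**The case against.** The strongest reply is that path b is described very briefly, with no covariates or random effects at all, so silence about condition is not proof that it was left out. That is fair as to what was actually fitted. It does not rescue the plan, because the same section spells out the interactions for Aim 1, and the definition given for path b contains the mediator alone.

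H2 can also be read as a claim about levels: tailoring targets barriers, so mediators improve in that arm and stay unfavourable in the other. Path a tests that, and the plan does not say which reading is meant. This stands as a limit on the moderation argument. But the declared goal is mediation of the condition effect, and for that path b still needs condition.

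A reader might go further and infer that H2 cannot be tested at all. The documents do not support this: the theme-valence comparison in C13b bears on H2, although it is not a mediation test. Nor do they support saying that opposite effects always cancel, since that needs roughly equal and opposite slopes with similar mediator spread. It is also tempting to say that the deviation reasons exist for month 1 only, or that the instrument mismatch blocks the aim. Table 5 and Section VII point to later collection, and Section VII lists other organizational measures and repeats its battery at 5 months. These are inconsistencies to reconcile.

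**Conclusion.** The point holds in a limited form. As described, path b estimates one mediator slope pooled over arms and unadjusted for condition. The arm-specific effect in H2 is therefore not tested by the quantitative models, and b is open to bias under either reading of H2.

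The size is illustrative only. Opposite slopes of 0.5 average to 0.00 and are detected at about the error rate; unequal slopes give a misleading average. The spurious slope from omitting condition is 0.05 to 0.17 over the assumed range, modest at the lower end beside slopes of .2 to .4. The slopes, encounter counts, outcome variances, mediator shifts and direct effects behind these figures are assumptions.

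The client-level gap is real on the text alone. Aim 2 is exploratory, so this is a correction that should be made, and it does not threaten the co-primary comparison.

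**What to change.** State path b as condition, mediator and condition x mediator, with clinic and clinician random intercepts, and report arm-specific slopes and indirect effects. Condition as a main effect alone removes the confounding but does not test the arm-specific reading. Say which reading of H2 is meant. Label the analysis exploratory. Much of C13a is in the past tense and reports that 22.8% of patients missed the 12-week interview; if Aim 2 has already been run, label the added terms post hoc.

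Fit the corresponding path for week-12 PHQ-9, or withdraw the client-level mediation claim and its kappa-squared of .10.

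Reconcile the collection window for deviation reasons (C6 and C12a against Table 5 and Section VII) and the instruments (Table 5 against the Section VII battery). Use as mediators only measures available at the 5-month assessment.

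No new data are needed for the two added terms; the cost is revised text and, if already analysed, a re-analysis. The statistical downside is wider intervals and possibly modest interaction power with 6 sites per arm. That power depends on the assumed ICC and should be stated: for slopes of +0.3/-0.3 the figures above run from 41% to 95% before site clustering.
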